12.0 CRITERIA FOR THERAPEUTIC RESPONSE/OUTCOME ASSESSMENT

Primary Specific Aim:

- To determine the change in estradiol and FSH from baseline to twelve weeks in postmenopausal women receiving adjuvant aromatase inhibitors during treatment with low dose vaginal 10 μ g 17- β estradiol.

Secondary Specific Aims:

- To compare the rise in estradiol in women on letrozole vs. anastrozole during treatment with low dose vaginal 10 μ g 17- β estradiol to see if there are differences between aromatase inhibitors.
- To describe patterns of estradiol and FSH levels over the twenty-four week study period.
- To compare the patient's FSFI scores at baseline, week 12 and week 24

Both FSH and estradiol levels will be measured in the clinical chemistry laboratory at MSKCC. Conventional FSH assays will be used. However, use of conventional estradiol assays is not appropriate due to inaccuracies in measuring serum estradiol levels <25 pmol/l.

The study will be called “VAG” with a unique five digit identification number for each patient (for example VAG-123456). The specimens will be anonymized and no name will be needed. Each time a specimen is received for an individual, the same identifier (for example VAG-12345) will be used. The first digit after VAG will indicate the site where the subject was consented. (1 for Gynecology at 53rd Street, 2 for Breast at 66th Street, 3 for Commack, 4 for Basking Ridge, 5 for Rockville Center, 6 for Sleepy Hollow.) Only the date and comment (for example - baseline, 2 weeks, 7 weeks, etc) will be specific for the time relative to treatment. The specimen will be sent to the lab with a paper requisition since the panel will not be ordered in OMS. The specimens will be accessioned, aliquoted, tested and the results will be available on the hospital computer that is not accessible to the clinicians running the study (results are blinded).

The FSH will be run in real time and the estradiol will be stored frozen until assay. Stability of the specimen is not a problem. Estradiol will be assayed in a batch mode and the turnaround time is to be determined – depending on the rate of accrual. The FSH will be performed on the Siemens Centaur XP (an automated immunoassay analyzer system). At present we are planning to perform the ultrasensitive estradiol by a manual RIA procedure. Use of conventional estradiol assays is not appropriate in this patient group due to inaccuracies in measuring serum estradiol levels <25 pmol/l. Therefore, serum estradiol levels will be measured using a more sensitive radioimmunoassay, which can accurately quantify the low levels of estradiol seen in postmenopausal women being treated with aromatase inhibitors. The assay will be done by a commercially available RIA kit from Diagnostic Systems Laboratories (Beckman Coulter Company). This test is specifically formulated as an Ultra-Sensitive estradiol assay. The assay measures estradiol in pg/ml and the assay sensitivity is 2.2 pg/ml. The estradiol assays will be run in batch mode depending on the accrual rate for the specimens. Assaying serial specimens in the same run will eliminate inter-assay variation. Specimen degradation and freeze thawing are not a problem since estradiol is a steroid hormone and extremely stable in serum/plasma.

There is an automated method under development on the Beckman Access automated analyzer that is “For Research Only” and if this assay becomes available and proves reliable, it would be a better and faster alternative. However, this method is still under development and not yet proven. The required specimen is serum (speckled Red top tube). The specimen should be centrifuged and the speckled tube sent to the Lab. No refrigeration is necessary. [name] will be responsible for supervising the tests.

13.0 CRITERIA FOR REMOVAL FROM STUDY

- If at any time the patient develops recurrent or progressive disease (e.g. a new breast primary, loco-regional or distant recurrence) she will be taken off study and referred for conventional therapy.

- If at any time the patient develops unacceptable toxicity, defined as any Vagifem related toxicity greater than or equal to a grade three toxicity, she will be removed from study.
- If at any time the patient is found to be ineligible for the protocol as designated in the section on Criteria for Patient/Subject Eligibility (i.e. a change in diagnosis), the patient will be removed from the study.

14.0 BIOSTATISTICS

This is a prospective longitudinal pilot study, and the targeted patient population is postmenopausal women with breast cancer being treated with adjuvant aromatase inhibitors who are initiated on vaginal 17 β -estradiol to relieve symptoms of atrophic vaginitis. These women have completed primary breast cancer treatment including surgery, radiation therapy, and chemotherapy with the exception of hormonal therapy and should have no evidence of disease. . One common symptom of breast cancer therapy is atrophic vaginitis. Recent literature has suggested that women with breast cancer who use estradiol vaginal tablets for the treatment of atrophic vaginitis have had spikes in serum estradiol. This is a potentially dangerous suggestion since breast tumors are often fueled by hormones. The published studies are observational and based on very small series of patients. The aim of this study is to prospectively evaluate this trend in a larger series of breast cancer patients who use vaginal estradiol tablets.

Serum estradiol levels and FSH levels will be assessed at baseline, and weeks 2, 7, 12, 18 and 24 during treatment with vaginal estradiol tablets. The bloodwork will take less than one hour to perform and will be drawn +/- 72hrs from the date the patient is due for bloodwork. Baseline bloodwork will be drawn within 14 days of study enrollment prior to the initiation of vaginal 10 μ g 17- β estradiol. Patients will be encouraged to come for their research bloodwork 12-24 hours after the insertion of the vaginal 10 μ g 17- β estradiol tablets. Patients will record in their diary the time of their last vaginal 10 μ g 17- β estradiol tablet insertion. FSFI (Female Sexual Function Index) is an overall measure of sexual function and is based on six domains: desire, arousal, lubrication, orgasm, satisfaction and pain.¹³ Along with the laboratory measurements of estradiol and FSH, the FSFI survey questionnaire and menopause symptom checklist will be administered at baseline, and the 12 and 24 week time points. The FSFI will take ten minutes and the menopause symptom checklist will take three minutes to complete. Both will be administered +/- 72hrs from the date the patient is due for the survey. The baseline FSFI and the menopause symptom checklist will be completed within 14 days of study enrollment prior to the initiation of vaginal 10 μ g 17- β estradiol.

The primary analysis will focus on analyzing the change in estradiol level from baseline to 12 weeks using a two-sided paired t-test. We plan to recruit sixty eligible women, with the expectation that 48 (80%) will complete the study and be compliant. We plan to recruit 30 women who have been on anastrozole therapy and 30 women who have been on letrozole therapy. Patients who drop out due to self-withdrawal, recurrence or noncompliance will be eliminated from the primary analysis but will be examined closely. Patients are evaluable if they have at least baseline and week 12 values.

The primary analysis will be a two-sided paired t-test to evaluate whether there was a change in estradiol levels from baseline to 12 weeks. For a sample size of 48, we will be able to detect a difference of .41 or higher on a standard unit scale with 80% power and **5% type I error** using a paired t-test. To translate this into the scale commonly used to report estradiol, we examine a series of 6 breast cancer patients published by Kendall et al (2006). In Kendall et al, estradiol levels ranged from close to 0 to 5 pmol/l before starting vaginal estradiol, to close to 0 to 25 at 7 weeks. Based on these data, we conservatively estimate the standard deviation of the difference to be 7 (**roughly, range/4**). Thus, for a sample size of 48 we will be able to detect an absolute difference in estradiol of 2.88 pmol/l with 80% power and **5% type I error**.

In addition to the main analysis described above, there are several secondary analyses planned for the FSH and FSFI/menopause checklist endpoints. Two-sided paired t-tests will be performed to evaluate change in FSH levels from baseline to 12 weeks and FSFI from baseline to 12 weeks and baseline to 24 weeks. To adjust for covariates of interest, such as type of aromatase inhibitor, an ANCOVA will be fit to the data. Trends of estradiol levels, FSH levels, and FSFI/menopause symptoms over the course of the study for all available timepoints will also be examined using graphical methods and repeated measures models. The graphs will illustrate patients and drug-specific short- and long term variations in estradiol (primary endpoint), FSH, and FSFI/menopause symptoms (secondary endpoints). It is hypothesized that estradiol levels will increase until approximately week 12 and then return to baseline after the vaginal walls reepithelialize. It is also hypothesized that FSH will remain constant throughout the 24 weeks and the FSFI/some menopausal symptoms will show improvement from baseline to both 12 and 24 weeks. To bring data from all these timepoints together, we will fit a repeated measures model²⁰ and if needed adjust our model to allow the time-effect to be modeled nonparametrically.²¹ Modeling the time-effect nonparametrically may be needed if estradiol trends over time, for example, do not have a simple parametric form such as a straight line or a quadratic curve. Model parameters and graphs of the raw data will help us identify where there are increases, decreases, or plateaus in estradiol, FSH, and FSFI over the study period. All these models can be fit in standard statistical software like SAS for Windows.

As in any prospective study, we expect missing data on a subject and item level. This is a small study, and thus, we do not plan to do any imputation. However, we will evaluate the degree of missingness in the final study by calculating attrition rates and the percent of missing values for a given variable. We will also examine the patient characteristics of the patients who have missing values. All analyses will be interpreted with missing data issues in mind.

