The primary specific aim is to determine the change in estradiol and FSH from baseline to twelve weeks in postmenopausal women receiving adjuvant aromatase inhibitors during treatment with low dose vaginal 10 μ g 17- β estradiol. A secondary specific aim is to compare the rise in estradiol in women on letrozole vs. anastrozole during treatment with low dose vaginal 10 μ g 17- β estradiol to see if there are differences between aromatase inhibitors. Another secondary specific aim is to describe patterns of estradiol and FSH levels over the twenty-four week study period. A third secondary aim is to compare the patient's FSFI score at baseline, weeks 12 and 24.

Patient Population: 60 postmenopausal breast cancer patients who have completed their primary treatment for breast cancer with the exception of endocrine therapy who are currently being treated with adjuvant aromatase inhibitors with no evidence of disease. 60 women are being recruited with the goal of obtaining 48 evaluable patients.

Study Design: This study is a prospective longitudinal pilot study measuring serum estradiol and follicle stimulating hormone (FSH) levels in 60 postmenopausal breast cancer patients currently receiving treatment with adjuvant aromatase inhibitors (30 being treated with letrozole and 30 with anastrozole) who are initiated on vaginal estrogen for symptoms of urogenital atrophy. After a patient elects to participate and provides informed consent, a blood sample will be obtained to measure baseline estradiol and FSH levels. Patients will then receive a prescription

for vaginal 10 μ g 17- β estradiol. We hypothesize that low dose vaginal 17- β estradiol is a potentially safe and effective intervention, which does not cause an elevation in serum estradiol levels at 12 weeks in postmenopausal breast cancer patients on aromatase inhibitor therapy. In addition to studying the primary endpoint of estradiol levels, we will also study FSH, and FSFI/menopause symptom checklist as secondary endpoints.

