Low dose vaginal 17- β estradiol was shown to be highly effective in treating menopausal urogenital atrophy in women without cancer.² Vaginal 17- β estradiol was designed to relieve symptoms of urogenital hypoestrogenism with minimal systemic absorption and improved ease of usage compared to other vaginal estrogen formulations. In a study comparing 17- β estradiol to vaginal estrogen cream, both methods were equivalent for relief of atrophic vaginitis symptoms, but patients using vaginal 17- β estradiol had less systemic estrogen absorption, less endometrial proliferation and greater overall satisfaction.³ In another study, vaginal 17- β estradiol caused vaginal maturation, which gradually diminished absorption and systemic "spill over" of estradiol.⁴ In postmenopausal women after fourteen days of treatment, maturation of the vaginal epithelium occurred and absorption of estradiol subsequently declined significantly. FSH levels were unchanged during treatment with the 17- β estradiol. When systemic estradiol levels increase, FSH levels decrease correspondingly. Given the results of these studies, it was felt vaginal 17- β estradiol was efficacious and safe even for women trying to avoid estrogens. Recently a lower dose, 10 mcg 17- β estradiol, was FDA approved for postmenopausal women and is now readily available.

Despite the prevalence of urogenital symptoms in women with breast cancer, treatments have not been well studied in this population and are limited to over the counter lubricants, moisturizers, and dilator use with minimal impact. Vaginal 17- β estradiol was initially considered to be efficacious and safe even for women trying to avoid estrogens, and became widely prescribed to patients with breast cancer including women on endocrine therapy. Studies evaluating vaginal 17- β estradiol in postmenopausal women without breast cancer found only a transient increase in estradiol levels with return to baseline within twelve weeks. However, a recent prospective small observational study (n=6) performed by Kendall et al. demonstrated elevation in estradiol levels in 5 out of 6 women on aromatase inhibitors after two weeks of treatment with 25 mcg 17- β estradiol.⁵ After twelve weeks of therapy, estradiol levels decreased, but returned to pre-treatment levels in only 2 out of 6 women, which calls into question the safety of low dose 17- β estradiol in women with breast cancer. . The concern is that using low-dose vaginal estrogens

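### Every planned estradiol estimate is a mean and no per-woman result is pre-specified, so large rises in about three or fewer of 48 women would usually leave the primary test non-significant

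*Combined protocol and SAP*

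**What the plan says.** All references are to the combined protocol and SAP.

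- **Motivation.** Section 14.0 cites literature that "women with breast cancer who use estradiol vaginal tablets for the treatment of atrophic vaginitis have had spikes in serum estradiol" and continues: "The aim of this study is to prospectively evaluate this trend in a larger series of breast cancer patients who use vaginal estradiol tablets". Section 3.0 reports the earlier series by counting women. Five of six were raised at week 2, and by week 12 estradiol had "returned to pre-treatment levels in only 2 out of 6 women".
- **Hypothesis.** Section 1.0 expects a treatment "which does not cause an elevation in serum estradiol levels at 12 weeks in postmenopausal breast cancer patients on aromatase inhibitor therapy".
- **Primary analysis.** Section 14.0: "The primary analysis will focus on analyzing the change in estradiol level from baseline to 12 weeks using a two-sided paired t-test". The power statement reads "For a sample size of 48, we will be able to detect a difference of .41 or higher on a standard unit scale" (power 80%, type I error 5%). Using an SD of 7, it converts this to 2.88 pmol/l.
- **Other analyses.** Section 14.0 adds an ANCOVA for covariates such as type of aromatase inhibitor, repeated measures models over all visits (with a nonparametric time effect if needed), and graphs of patient-level and drug-specific variation. Describing patterns over 24 weeks is a secondary aim in Section 2.0.
- **Data.** Section 4.2 schedules six estradiol values per woman (weeks 0, 2, 7, 12, 18 and 24).

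No section defines a raised individual value, a proportion of women with a rise, or a peak change.

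**The concern.** The safety question is whether some women absorb enough estradiol to show a rise. A paired t-test answers a different question: whether the average changed. A few large rises move the mean of 48 only slightly, and they also inflate the SD by which that mean is judged. The two effects largely cancel, so making the rises larger does not help the test.

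Timing matters too. In the earlier series most women were raised at week 2. A woman who is raised at week 2 or 7 and back to baseline by week 12 contributes a change of about zero to the primary test.

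At stake is what the trial can conclude. It is meant to follow up a series reported as so many women out of six, yet no result in that form is planned, and no interval would accompany one.

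**Working it through.** **1. The plan's own figure.** Paired t-test, n = 48, two-sided 5%, 80% power. The noncentral t distribution gives a detectable difference of 0.413 SD; 0.413 × 7 = 2.89 pmol/l. The plan states 0.41 and 2.88, so its figures reproduce. The normal approximation gives 0.404 and 2.83.

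**2. Inputs for the check.**
- Size of a rise: Section 14.0 quotes about 0 to 5 pmol/l before treatment and about 0 to 25 at week 7. I take S = 20 to 25 pmol/l. This is an assumption: that series used 25 mcg rather than 10 mcg, and I apply the week-7 range to week 12.
- Noise: the SD of the week-12 change in women with no true rise, assumed between 1 and 7 pmol/l. The upper end is the plan's SD.
- k = number of women out of 48 with a true rise; all others have mean change zero.

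**3. Without noise (exact).** Mean = kS/48 and t = √[k(n−1)/(n−k)], so S cancels. The critical value on 47 df is 2.01.
- k = 3: t = √(3 × 47/45) = 1.77, p = 0.083, whatever the size of the rise.
- k = 4: t = √(4 × 47/44) = 2.07, p = 0.044.

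**4. With noise (simulation of the planned test).** Chance that the test is significant for a rise:

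| Women with a rise | Mean change, pmol/l (S = 20 to 25) | Noise SD 2 | Noise SD 1 to 7 |
|---|---|---|---|
| 1 | 0.42 to 0.52 | 1 to 2% | 0 to 5% |
| 2 | 0.83 to 1.04 | 4 to 6% | 0 to 9% |
| 3 | 1.25 to 1.56 | 16 to 17% | 6 to 18% |
| 4 | 1.67 to 2.08 | 43 to 47% | 19 to 59% |
| 5 | 2.08 to 2.60 | 75 to 83% | 28 to 99% |
| 6 | 2.50 to 3.13 | 94 to 98% | 39 to 100% |

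With the overall SD held at the plan's 7 and S = 20, the figures are 14% for three women, 28% for four, 53% for five and 90% for six.

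**5. What a count would show.** Exact (Clopper-Pearson) 95% limits: 3/48 = 6.3% (1.3 to 17.2%); 0/48 has an upper limit of 7.4%. The chance that at least one such woman is among the 48 is 1 − 0.95^48 = 91% if the true rate is 5%, and 1 − 0.90^48 = 99% if it is 10%.

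**6. Why a count needs a margin.** Suppose a rise meant only a measurable value above baseline. For a woman whose values are all measurable and who has no drug effect, baseline is the highest of six exchangeable values one time in six. She would therefore be flagged at some visit 5/6 = 83% of the time. The assay limit of 2.2 pg/ml is about 8.1 pmol/l (2.2 × 3.671, the molar-mass conversion). A woman with a steady true level of 5 pmol/l would be flagged about 7% of the time if single values have SD 1.4, and about 26% if SD 2 (both assumed).

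**The case against.** The plan does more than test one mean. Section 14.0 models estradiol at every visit and plans patient-level graphs; three rises of 20 to 25 pmol/l from a baseline of 0 to 5 would be plain to see on them. The study calls itself a pilot, its stated aim is the change in estradiol, and the test matches that aim. Section 3.0 says the level that minimizes risk is unknown, so the documents offer no individual cut-off. If the new series resembled the old one, with most women raised, a test of the mean would find it easily.

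Much of this stands, and it rules out three stronger readings.

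- A reader might infer that the study looks only at the week-12 mean. That is true of the primary test alone. The secondary models and graphs use all visits, but the models still average over women and the graphs have no stated criterion, count or interval.
- A reader might infer that a non-significant test will be reported as no elevation. No passage says so. The hypothesis in Section 1.0, with no equivalence margin, invites that wording but does not commit the sponsor to it.
- A reader might infer that the trial could not be compared with the earlier series. Six values per woman are collected, so counts could be tabulated later; what is missing is a definition fixed in advance.

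The lack of a clinical threshold does not remove the need. A rise can be defined analytically, from assay and within-woman variation, without claiming clinical meaning.

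**Conclusion.** The concern holds in limited form. The primary test concerns a mean at one visit, and no per-woman estimate is pre-specified for a safety question posed about individual women. Large rises in three or fewer of 48 women would leave the t-test non-significant in roughly 82% or more of trials. It would be wrong to extend this to any small group of women: at four the result depends on noise, and at five or six the test often succeeds when noise is low to moderate. Rise size, noise and the number of women affected are assumptions; the three-woman result is stable across the ranges tried. The exclusion of rises that resolve before week 12 needs no assumption, because it follows from the definition of the primary endpoint. This is a worthwhile, inexpensive improvement and not a flaw that invalidates the planned test.

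**What to change.** Add a descriptive secondary table to Section 14.0 and keep the t-test as it is.

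- **Content:** the number and percent of women with a rise at each of weeks 2, 7, 12, 18 and 24 and at any visit, with exact 95% confidence intervals and the number of women with a value at each visit, plus each woman's peak change.
- **Definition, fixed before unblinding:** a value that is measurable (at or above 2.2 pg/ml) and exceeds the woman's own baseline by more than a stated margin. An unmeasurable baseline is set to the assay limit. The margin should come from assay and within-woman variation. State that this is an analytical definition, not a clinical cut-off.
- **Wording:** say that a non-significant t-test is evidence about the mean change only.

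The cost is one more descriptive endpoint and one table from data already scheduled, with no new samples, visits or patients. The documents give no precision figure for the assay beyond its sensitivity, so the laboratory would have to supply the basis for the margin. Rises below the assay limit or within the margin would not be counted, and the table should say so.

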4.0 OVERVIEW OF STUDY DESIGN/INTERVENTION

4.1 Design

This study is a prospective longitudinal pilot study measuring serum estradiol levels in 60 breast cancer patients in order to obtain 48 evaluable patients currently receiving treatments with adjuvant aromatase inhibitors. The goal is to have 30 patients on letrozole and 30 on anastrozole who are initiated on vaginal estrogen for symptoms of urogenital atrophy. Eligible women (see eligibility criteria section 6.0) seen in either breast medicine or gynecology clinic at MSKCC will be counseled on the use of low dose vaginal estrogens for symptomatic relief. A member of the clinical research staff will invite patients interested in using vaginal estrogens to participate in the study. After a patient elects to participate and provides informed consent, we will obtain serum to measure baseline estradiol and follicle stimulating hormone (FSH) levels. Patients will also complete the FSFI questionnaire. Patients will then receive a prescription for 10mcg vaginal 17- β estradiol.

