All subjects will receive 10mcg vaginal 17-β estradiol tablets. The primary endpoint will be change in estradiol and FSH from baseline to 12 weeks. Each subject will serve as her own control. We will monitor serum estradiol and follicle stimulating hormone (FSH) levels closely from 0-24 weeks. We will measure serum estradiol and FSH levels at baseline, and subsequently at weeks 2, 7, 12, 18 and 24 after commencing therapy with 10mcg vaginal 17-β estradiol. The bloodwork will take less than one hour to perform and will be drawn +/- 72hrs from the date the patient is due for bloodwork. Baseline bloodwork will be drawn within 14 days of study enrollment prior to the initiation of vaginal 10 µg 17- β estradiol. Patients will be encouraged to come for their research bloodwork 12-24 hours after the insertion of the vaginal 10 µg 17- β estradiol tablets. Patients will record in their diary the time of their last vaginal 10 µg 17- β estradiol tablet insertion. Since we do not know the clinical significance of transient estradiol elevation in these patients, both the patients and the investigators will be blinded to the results of these assays for the 24 weeks of study therapy. This will also help avoid patient and investigator bias. Results will be unblinded after accrual is complete and all patients have completed the 24 weeks of planned therapy. At week 24, all patients go off study, but patients can choose to remain on vaginal 17-β estradiol or discontinue the treatment. Patient's estradiol levels may continue to be monitored for the duration of her treatment with vaginal 17-β estradiol at her physician's discretion and depending on the findings of this study. We will continue to collect this data if the patient is being followed at MSKCC. Patients can choose to remain on it for as long as they desire.

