7.0 RECRUITMENT PLAN

Women at breast medicine oncology clinics and gynecology clinics at Memorial Sloan-Kettering Cancer Center (MSKCC) will be identified by their treating physicians as potential research subjects. If the investigator is a member of the treatment team, s/he will discuss the study with the patient. Otherwise the patient will be referred to an investigator.

During the initial conversation between the investigator/research staff and the patient; the patient may be asked to provide certain health information that is necessary to the recruitment and enrollment process. Specifically, patients will be asked about symptoms related to urogenital atrophy. The investigator/research staff may also review portions of her medical records at MSKCC in order to further assess eligibility. They will use the information provided by the patient and/or medical record to confirm that the patient is eligible and to contact the patient regarding study enrollment. If the patient turns out to be ineligible for the research study, the research staff will destroy all information collected on the patient during the initial conversation and medical records review, except for any information that must be maintained for screening log purposes. If the woman agrees to study participation, a consenting individual (listed below in section 15.1) will obtain informed consent from the patient until a goal of 60 eligible patients are entered into the study in order to have 48 evaluable patients.¹⁸

In most cases, the initial contact with the prospective subject will be conducted either by the treatment team, investigator or the research staff working in consultation with the treatment team. The recruitment process outlined presents no more than minimal risk to the privacy of the patients who are screened and minimal PHI will be maintained as part of a screening log. For these reasons, we seek a (*partial*) limited waiver of authorization for the purposes of (1) reviewing medical records to identify potential research subjects and obtain information

relevant to the enrollment process; (2) conversing with patients regarding possible enrollment; (3) handling of PHI contained within those records and provided by the potential subjects; and (4) maintaining information in a screening log of patients approached (if applicable).

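### The primary analysis set is ambiguous for women who give baseline and week-12 estradiol samples and then drop out in weeks 13–24.

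*Combined protocol and SAP*

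**What the plan says.** Section 14.0 makes the primary analysis a two-sided paired t-test of the change in estradiol from baseline to week 12. Two adjacent sentences then decide who is in it. The first removes women: "Patients who drop out due to self-withdrawal, recurrence or noncompliance will be eliminated from the primary analysis but will be examined closely". The second admits them: "Patients are evaluable if they have at least baseline and week 12 values".

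The planned 48 women are described in two ways. Section 14.0 gives the recruitment target of sixty "with the expectation that 48 (80%) will complete the study and be compliant". The protocol summary (1.0) says "60 women are being recruited with the goal of obtaining 48 evaluable patients", the design section (4.1) has "60 breast cancer patients in order to obtain 48 evaluable patients", and the recruitment plan (7.0) has "a goal of 60 eligible patients are entered into the study in order to have 48 evaluable patients".

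On timing, section 4.1 says "At week 24, all patients go off study", and section 4.2 continues maintenance treatment to that point. Section 13.0 takes a woman off study for recurrence whenever it occurs. On blinding, section 4.1 says "Results will be unblinded after accrual is complete and all patients have completed the 24 weeks of planned therapy".

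**The concern.** The endpoint closes at week 12, and follow-up continues for another 12 weeks. A woman can therefore supply a complete baseline-to-week-12 pair and afterwards withdraw, recur or become noncompliant. Read literally, the elimination sentence removes her from the primary test, while the sentence after it counts her as evaluable. Two statisticians could build different primary sets and each cite section 14.0.

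What is at stake is the estimate of the week-12 rise. Dropping an observed pair because of something that happened later cannot improve that estimate, since later behaviour cannot alter a sample already taken. It loses precision. It may also select on events related to exposure: losing women with larger rises understates the mean rise, and losing women with smaller rises overstates it. The study is single-arm, with each woman as her own control, so there is no comparator in which such selection might partly cancel.

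**Working it through.** **1. The text.** Take a woman with both samples who withdraws in week 15.
- Elimination sentence: she dropped out for a listed reason and no time limit is given, so she is out.
- Evaluability sentence: she has both values, so she is in.
- No section gives either sentence precedence or limits elimination to the period before the week-12 sample. The expectation about completing the study points to week 24; the evaluability definition points to week 12.
- The elimination sentence names only self-withdrawal, recurrence and noncompliance. Removal for grade 3 or higher toxicity or for ineligibility (13.0) is not named, so the ambiguity is confined to the three listed reasons.

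**2. The plan's own figures.** Inputs from 14.0: n = 48, two-sided alpha 5%, SD of the difference 7 pmol/l, detectable difference 0.41 SD or 2.88 pmol/l, 80% power.
- Recruitment: 48/0.80 = 60, as stated.
- Exact (noncentral-t) detectable difference at n = 48 and 80% power: 0.413 SD; 0.413 × 7 = 2.89 pmol/l.
- Power at 2.88 pmol/l, SD 7, n = 48: 79.7%.

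The stated figures reproduce.

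**3. How far the two readings can differ in number.** The plan expects 60 − 48 = 12 losses and does not say how many fall after week 12. If none do, both readings give 48. If 6 do, the readings give 48 and 54. If all 12 do, they give 48 and 60. Keeping late drop-outs can only add pairs to the planned 48.

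**4. Possible effect on the estimate (assumed inputs).** Take N = 54 women with both values, a true mean rise of 2.88 pmol/l among all 54, and k women eliminated whose mean change differs from the others' by a gap of 0.5 SD = 0.5 × 7 = 3.5 pmol/l.
- Shift in the mean = (k/N) × gap.
- k = 2: 2/54 × 3.5 = 0.13 pmol/l. Standard error with the remaining 52: 7/√52 = 0.97.
- k = 6: 6/54 × 3.5 = 0.39 pmol/l. Standard error with the remaining 48: 7/√48 = 1.01.

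A gap between groups adds variance, so power is given under two conventions, with p = k/N: (A) SD 7 within groups, so that the full-set SD is √(49 + p(1−p)·gap²); (B) SD 7 in the full set, so that the within-group SD is √(49 − p(1−p)·gap²). For k = 2 these SDs are 7.03 and 6.97; for k = 6 they are 7.09 and 6.91.

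| Eliminated | Convention | All 54 kept | Eliminated women 0.5 SD higher | Eliminated women 0.5 SD lower |
|---|---|---|---|---|
| 2 (n = 52) | A | 84.0% | 79.4% | 86.0% |
| 2 (n = 52) | B | 84.3% | 79.7% | 86.3% |
| 6 (n = 48) | A | 83.5% | 67.5% | 88.7% |
| 6 (n = 48) | B | 84.3% | 68.6% | 89.4% |

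With no gap there is no bias and only sample size is lost: 84.3% to 82.9% for k = 2, and 84.3% to 79.7% for k = 6. The rise in power when the gap is reversed is not a benefit; it comes from an overstated mean.

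**The case against.** The strongest reply is that the sentences have a natural joint reading. The paragraph opens with the change to week 12, the second sentence is the only definition of evaluability, and its wording signals that later values are not needed. Drop-out would then mean before the week-12 sample. The expectation about completing the study can likewise be taken as a recruitment forecast and not as a set definition. This stands to the extent that the point is an ambiguity; a reader might infer an outright contradiction, and the documents do not support that. The ambiguity remains because no section states the joint reading.

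The loss is also limited. Section 14.0 plans repeated measures models over all available timepoints, and the elimination sentence is confined to the primary analysis. A late drop-out's values therefore still enter those models, and only the primary paired t-test loses them. Attrition and the characteristics of women with missing values will be reviewed, and reasons for stopping are recorded (10.0). These safeguards are real, but they do not say who is in the primary set.

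A reader might infer that the set could be picked to suit the result. Nothing suggests that this is intended. Patients and investigators are blinded to the assays until all women finish 24 weeks (4.1), and results sit on a system closed to the study clinicians (12.0). Blinding also means the rule can still be fixed before estradiol is seen.

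Finally, a woman who is noncompliant before week 12 but still gives a week-12 sample raises a separate and more debatable question, because noncompliance is not defined. It is not part of this point.

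**Conclusion.** The point holds as an ambiguity in the primary analysis set. It is worth correcting because the elimination sentence, followed as written, would discard observed primary-endpoint pairs on account of events after the endpoint.

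Its size is probably small and cannot be settled from the documents, which give neither the number of drop-outs after week 12 nor how their changes differ. With 2 of 54 eliminated at a 0.5 SD gap, the shift is about 13% of the standard error (0.13/0.97). The 6-of-54 case needs half of the 12 planned losses to fall after week 12 and their mean change to differ by the full 0.5 SD.

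Two stronger inferences are not supported. The sample size is not wrong: the plan is powered on 48 whichever sentence governs. Nor can it be said that the rise would be understated, because the direction of any selection is unknown.

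**What to change.** In section 14.0:
- State that every woman with baseline and week-12 estradiol values is in the primary paired t-test, whatever withdrawal, recurrence or noncompliance occurs after the week-12 sample.
- Limit the elimination sentence to events before that sample.
- Describe the 48 throughout as women with both values, replacing the expectation about completing the study and compliance.

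Make the change before the estradiol results are unblinded. The cost is a wording change, with no extra patients, visits or assays.
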